### **7.3. Measures of Treatment Compliance**

Time on treatment (days) will be defined, for each Part/Period, as (date of last dose - date of first dose + 1). Dose interruptions will be subtracted from this calculation.

Patients will strive for 100% compliance with the daily dosing schedule. Treatment compliance will be summarized as percent of planned dose received for each dosing regimen. Percent of planned dose received will be calculated for each Part/Period as follows:

- $100 * (\text{Tablets Dispensed} - \text{Tablets Returned}) / (\text{Tablets Expected})$

Tablets Expected is defined as the time on treatment multiplied by the expected number of pills taken daily (x2 for the 12 mg BID group; x2 for the 8 mg BID group; x2 for the 4 mg BID group; x2 for the placebo group), where time on treatment is defined as above, but with dose interruptions being ignored in this calculation. Derived patient compliance, compliance per the eCRF (80% or higher versus less than 80%), and dosing exceptions will be listed in by-patient data listings.

## 8. ENDPOINT EVALUATION

### 8.1. Overview of Efficacy Analysis Methods

#### 8.1.1. Multicenter Studies

Patients will be enrolled at up to approximately 25 sites; site identifiers will be included in by-patient listings.

#### 8.1.2. Assessment Time Windows

The visit schedule for all study assessments is provided in Appendix 15.2, by Part. For scheduled visits, there will be no reassignment of the analysis visit based on date. Unscheduled visits and early termination visits will be reassigned based on the analysis windows in the below table and the schedule of events. Assessments in part B will be windowed counting from the part B treatment start date. Assessments may only be re-assigned to visits where they were to be collected per the schedule of events. The latest assessment in a window will be selected as the visit used in summaries, unless otherwise specified. All visits will be included in by-patient data listings.

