Event	Day -28 to Day -1 (Visit 1)	Randomization ^{1, 2} Day 1 (Visit 2)	Week 2 (Visit 3)	Week 4, 8 (Visit 4, 5)	Week 12 (Visit 6)	Week 16, 20 (Visit 7, 8)	Week 243,4 (Visit 9)	Week 28 ⁵ (Visit 10)	Week 32 (Visit 11)	Week 36 (Visit 12)	Week 40, 44 (Visit 13, 14)	Week 484 (Visit 15)	Safety Follow-Up Visit
Informed consent	X												
Eligibility assessment	X	X											
Demographics	X												
Medical history	X	X											
Randomization		X					X^7						
PE	X	X					X					Х	X
Brief PE				X	X	X			X	X	Х		
Height	X												
Weight	X	X		X	X	X	X		X	X	X	X	X
Pregnancy test ⁸	X	X ⁹		X	X	X	X	X	X	X	X	X	
Tuberculosis test	X												
Clinical laboratory testing ¹⁰ , 11	X ¹²	X	X	X	X	X	X	X	X	X	X	X	X
Lipid assessment ¹³		X			X		X			X		X	X
HBV and HCV test	Х												
12-lead electrocardiogram	Х	X			Х		X			X		Х	X
Vital signs	X	X		X	X	X	X		X	X	Х	X	X
SALT assessment	Х	X		X	X	X	X	X^{14}	X^{14}	X^{14}	X14	Х	
Photographs	X	X		X	X	X	X	X	X	X	Х	X	
SPRO and QPRO		X			X	X	X						
CGI-S and PGI-S		X			Х	X	X						
CGI-I and PGI-I					X	X	X						
Dispense study drug		X		X	X	X	X^7	X^{15}	X^{15}	X^{15}	X15		
Pharmacokinetic blood sampling ¹⁶		X			X		X						
Study drug accountability				X	X	X	X		X	X	X	X	_
Adverse events	X				X					X			X
Concomitant medications	X		X			X				X			

PE = Physical Examination; HBV= hepatitis B virus; HCV = hepatitis C virus; SPRO = Satisfaction of Hair Patient Reported Outcome; QPRO = Quality of Hair Patient Reported Outcome; CGI-S = Clinical Global Impression of Severity; CGI-I = Clinical Global Impression of Improvement; PGI-S= Patient Global Impression of Improvement; PGI-I = Patient Global Impression of Improvement;

- ¹ Day 1 (Visit 2) may occur any time after Screening laboratory results are available and reviewed by the Investigator.
- ² For Part A, Period 1, all subsequent visits and week increments should be based on the date of Visit 2. All visit windows are ± 2 days.
- ³ Week 24 from Part A, Period 1 will also serve as the Day 1 visit for Part A, Period 2 for those who meet criteria to continue into the Dose Modification Phase.
- ⁴ Also serves as the Early Termination Visit for patient withdrawal in this period.
- ⁵ For Part A, Period 2, all subsequent visits and week increments should be based on the date of Week 24 (Visit 9). All visit windows are ±2 days.

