10.2.1. Dose Interruption Safety Criteria and Management

Patients who experience hematologic adverse events as described in Table 3, significant clinical laboratory abnormality, or adverse events that may reflect an unfavorable risk-benefit profile may have their dose interrupted at the discretion of the Investigator. The Medical Monitor should be consulted whenever possible prior to decisions for dose interruption.

Patients who withdraw consent and therefore are discontinued from the study should undergo an Early Termination Visit and subsequent Safety Follow-up Visit as appropriate per Section 9.3.1 Patient Withdrawal Procedures, and associated adverse events followed as described in Section 12 Adverse Events.

Hematology parameters will be assessed bi-weekly for the first 4 weeks of the Treatment Period, and every 4 weeks thereafter for the remainder of the study. Prior to dose interruption, hematology parameters should be confirmed with repeat testing at an Unscheduled Visit within 72 hours, except in severe cases (i.e.: neutrophil counts below 0.5 x 10⁹/L) where immediate interruption of dosing is necessary for the safety of the patient. Blood draws confirming dose interruption criteria should occur prior to the first daily dose on the day of draw.

Dose interruption requirements for hematologic abnormalities are provided below. However, less significant changes may warrant clinical intervention and the Investigator should use his/her best clinical judgment when considering a dose interruption whether for singular or aggregate

hematology results above the limits provided in Table 3, or for other clinical signs, symptoms, or considerations that suggest dose interruption is in the best interest of the patient.

Table 3: Selected Hematologic Thresholds for Dose Interruption

Neutrophil Count	Dose Adjustment
Between 0.5 to 1 x 10 ⁹ /L	Interrupt dose until recovered to greater than 1.5 x 10 ⁹ /L and
(Grade 3)	resume dosing at previous dose
Less than 0.5 x 10 ⁹ /L (Grade 4)	Severe case: Interrupt dose immediately and repeat CBC with differential within 72 hours. Recommend hematology consult and contact medical monitor. Permanent discontinuation of treatment should occur upon repeat confirmation of value
Female Hemoglobin Level	Dose Adjustment
Less than 10 g/dL	Interrupt dose until recovered to greater than 10.5 g/dL and resume dosing at previous dose
Male Hemoglobin Level	Dose Adjustment

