**Table 2: Analysis Windows for Unscheduled and Early Termination Visits**

	Nominal Visit	Safety Analyses			Efficacy Analyses		
		Lower	Target	Upper	Lower	Target	Upper
Part A, Period 1	Screening	-28	-1	-1	-28	-1	-1
	Visit 2-Randomization	1	1	1	1	1	1
	Visit 3-Week 2	2	15	22	12	15	18
	Visit 4-Week 4	23	29	43	26	29	32
	Visit 5-Week 8	44	57	71	54	57	60
	Visit 6-Week 12	72	85	99	82	85	88
	Visit 7-Week 16	100	113	127	110	113	116
	Visit 8-Week 20	128	141	155	138	141	144
Part A, Period 2	Visit 9-Week 24	156	169	183	166	169	172
	Visit 10-Week 28 (PAP2 Week 4)	184	197	211	194	197	200
	Visit 11-Week 32 (PAP2 Week 8)	212	225	239	222	225	228
	Visit 12-Week 36 (PAP2 Week 12)	240	253	267	250	253	256
	Visit 13-Week 40 (PAP2 Week 16)	268	281	295	278	281	284
	Visit 14-Week 44 (PAP2 Week 20)	296	309	323	306	309	312
	Visit 15-Week 48 (PAP2 Week 24)	324	337	351	334	337	340
Part B	Visit B1-Day 1	1	1	1	1	1	1
	Visit B2-Week 2	2	15	22	12	15	18
	Visit B3-Week 4	23	29	43	26	29	32
	Visit B4-Week 8	44	57	71	54	57	60
	Visit B5-Week 12	72	85	99	82	85	88
	Visit B6-Week 16	100	113	127	110	113	116
	Visit B7-Week 20	128	141	155	138	141	144
	Visit B8-Week 24	156	169	183	166	169	172

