#### **9.5. Clinical Laboratory Evaluation**

Clinical laboratory samples should be collected at the beginning of each clinic visit and just prior to a dose on all Study Visit Days and will be processed by a central laboratory. In the event a

Concert Pharmaceuticals, Inc.  
Statistical Analysis Plan – CP543.2004

patient is unable to attend an in-clinic visit due to COVID-19, clinical laboratory blood draws may be performed by a Home Health Care agency or a local laboratory.

Clinical laboratory variables will be presented in 4 main ways, for each Part/Period of the study. First, change from baseline to each scheduled visit. Only post-baseline values on treatment (i.e., on the same date or prior to last dose of study drug) will be eligible for change from baseline calculations. Summary statistics for the mean and mean change from Part A Period 1 baseline will be reported for Part A Period 1, Part A Period 2, and Part B. The mean and mean change from Part A Period 2 baseline will be reported for Part A Period 2 and Part B. The mean and mean change from Part B baseline will be reported for Part B

Second, treatment-emergent potentially clinically significant (PCS) laboratory values will be identified. Potentially clinically significant values are defined as those that meet Grade 3 or Grade 4 toxicity criteria from the CTCAE criteria (or Grade 2 or higher for platelets). Laboratory values will be graded using CTCAE version 5.0, for those values included. CTCAE grades will be based solely on numeric results and without regard to other symptoms based on clinical judgment. For laboratory parameters whose CTCAE grading is independent of baseline criteria, treatment-emergent PCS laboratory values are those in which the baseline value is not PCS and the post-baseline value is PCS. For laboratory parameters whose CTCAE grading is dependent upon baseline criteria, any post-baseline grading of Grade 3 or Grade 4 (or Grade 2 or higher for platelets) will be considered treatment-emergent. The number and percentage of patients with treatment-emergent PCS laboratory values will be summarized by treatment group and overall for each clinical laboratory variable patient to CTCAE grading. For this analysis, the visit with the highest CTCAE grade value within a window will be selected.

Third, box plots of hemoglobin, platelets, and neutrophils will also be provided with dose interruption limits included as reference lines (see Protocol Section 10.2.1).

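### SAP 8.1.2 lets triggered unscheduled values displace scheduled ones in by-visit laboratory summaries, and SAP Table 2 runs the Week 24 safety window about two weeks past re-randomisation

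*SAP*

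**What the plan says.** SAP 8.1.2 sets three rules. For scheduled visits: "For scheduled visits, there will be no reassignment of the analysis visit based on date". For the rest: "Unscheduled visits and early termination visits will be reassigned based on the analysis windows in the below table and the schedule of events". Where several values share a window: "The latest assessment in a window will be selected as the visit used in summaries, unless otherwise specified". All visits go into the listings.

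SAP 9.5 states one exception. The treatment-emergent PCS tables take the highest CTCAE grade in the window. It gives no exception for mean change from baseline, for the counts of abnormal values, or for the figures, where "box plots of hemoglobin, platelets, and neutrophils will also be provided with dose interruption limits included as reference lines".

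Protocol 10.2.1 explains why unscheduled laboratory visits occur: "Prior to dose interruption, hematology parameters should be confirmed with repeat testing at an Unscheduled Visit within 72 hours", except in severe cases. After an interruption, the parameter is followed at least weekly until it recovers or 21 days have passed.

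On the clock, SAP 8.1.2 says: "Assessments in part B will be windowed counting from the part B treatment start date". It has no such sentence for Period 2, and Table 2 runs the Part A day count on without a break to Day 351. Protocol Table 1, footnote 5, times Period 2 visits from Visit 9 (Week 24), which footnote 3 makes Day 1 of Period 2 for continuing patients.

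**The concern.** Unscheduled laboratory values are not a random sample of times. Many exist because a scheduled value was abnormal. A rule that always takes the later value lets the triggered value stand for the visit and removes the triggering value from the summary. The box plots are the clearest case, since they are meant to show values against the interruption limits and the rule can remove a point that crossed one. The Part A haematology mean-change tables, abnormal counts and box plots are all marked in SAP 15.4 for the abbreviated report that supports the NDA.

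The second issue is attribution. At Week 24 responders move to a lower dose or placebo. If the Week 24 window stays open after that, a value taken on Period 2 treatment can be tabulated as a Period 1 result under the original dose.

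**Working it through.** **1. Reproducing SAP Table 2.** Target day = 7 × week + 1, counted from Period 1 Day 1. Safety upper limit = midpoint between this target and the next (the last row assumes a further 28 days). Safety lower limit = previous upper limit + 1.

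- Week 24: target 7 × 24 + 1 = 169. Upper limit (169 + 197)/2 = 183. The Week 20 upper limit is (141 + 169)/2 = 155, so the lower limit is 156.
- Week 28 (Period 2 Week 4): target 197, lower limit 184, upper limit (197 + 225)/2 = 211.

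All 13 rows from Week 2 to Week 48 reproduce exactly on this single count, so Period 2 is on the Period 1 clock.

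**2. Does a triggered value share the scheduled value's window?** Take an abnormal value on the target day, a retest 3 days later (72 hours), and weekly follow-up counted from the retest.

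- Week 4: scheduled Day 29, retest 29 + 3 = 32, follow-up 32 + 7 = 39. The window closes on Day 43. The next follow-up, Day 46, falls outside.
- Later visits: upper limit = target + 14, so target + 3 and target + 10 are inside and target + 17 is outside.
- Week 2: Day 15, retest Day 18, window closes Day 22. The follow-up on Day 25 is outside.

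The retest shares the window at every visit from Week 2 to Week 48, and one weekly follow-up shares it from Week 4 on. The Part B rows have the same limits as Period 1, so the same holds there.

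**3. Which outputs take the latest value?**

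| Output | Value used | Affected? |
|---|---|---|
| Laboratory mean change by visit (SAP 9.5) | Latest in window | Yes |
| Abnormal counts by visit (SAP 9.5, 15.4) | Latest in window | Yes |
| Haemoglobin, platelet, neutrophil box plots (SAP 9.5) | Latest in window | Yes |
| PCS tables (SAP 9.5) | Highest grade in window | No |
| Adverse event and dose-interruption tables (SAP 9.3) | Adverse event records | No |
| Listings (SAP 8.1.2) | All visits | No |
| Period 2 baseline (SAP 4) | Last value on or before the Period 2 dosing day | No |
| Part A co-primary (SAP 8.2.1) | Last observed Period 2 SALT | No |

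**4. Days of the Week 24 safety window after re-randomisation.** The window has 183 − 156 + 1 = 28 days. Visit 9 may fall 2 days either side of Day 169.

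| Re-randomised on | Window days afterwards | Week 28 window opens on Period 2 Day |
|---|---|---|
| Day 167 | 183 − 167 = 16 | 184 − 167 + 1 = 18 |
| Day 169 | 183 − 169 = 14 | 184 − 169 + 1 = 16 |
| Day 171 | 183 − 171 = 12 | 184 − 171 + 1 = 14 |

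With re-randomisation on target, an unscheduled value on Period 2 Days 2 to 15 maps to Week 24. The two issues meet here. An abnormal Week 24 value in a responder would be retested by Day 172 and followed up on Day 179. Both days come after the dose change, and both are inside the Week 24 window.

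**5. Does the on-treatment filter prevent this?** SAP 9.5 limits laboratory change from baseline to values on or before the last dose, without saying whether that means the last dose of the Period or of the study. Under the study reading, Days 170 to 183 pass. Under the Period reading, SAP 4 moves the Period 1 end date back one day when it coincides with the Period 2 start (169 − 1 = 168). That excludes Days 170 to 183, but it also excludes the Week 24 visit's own sample on Day 169. Neither reading covers the abnormal counts, or the vital sign and ECG summaries.

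**The case against.** The strongest reply is that the important safety signals do not pass through this rule. PCS tables take the worst grade, clinically significant results become adverse events (protocol 11.10), events causing interruption have their own tables, and every value is listed. The study is descriptive with no hypothesis tests. All of this stands, and it confines the point to the by-visit summaries marked in step 3.

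A reader might infer that recovered values systematically overwrite abnormal ones, so that the tables are biased toward normal. The documents do not support that. The retest normally comes before interruption, with the patient still on drug. A normal retest is then a failed confirmation rather than a recovery, and a confirming or worse retest would be selected just the same. About one further weekly value reaches the same window. The documents give neither the frequency of such events nor the size of any rebound.

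The Week 24 issue is also narrow. It touches only unscheduled or early-termination values in re-randomised responders, planned as about 50 per dose group, or 100 of 300. Giving the scheduled value priority would settle it wherever the Visit 9 value exists. That is correct, and it leaves the clock change to deal with missing values and consistent labelling.

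A reader might also extend the point to efficacy, because the SALT windows are only 3 days either side of target. That does not follow. The co-primary uses the last observed SALT whatever the window. Loss of maintenance is defined only in Period 2 and the mixed model is fitted only in Period 1, so no such value could be lost from that model. A wider SALT window trades gaps for mislabelled times, and the narrow choice is defensible.

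**Conclusion.** The point holds for two defined gaps in the SAP. First, the latest-in-window rule lets a triggered unscheduled value displace the scheduled one in the by-visit laboratory mean changes, the by-visit abnormal counts and the haematology box plots. Neither size nor direction can be fixed from the documents, so no figure is attached. The case rests on the selection rule being applied as written and on the retest timing in protocol 10.2.1.

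Second, half of the Week 24 safety window (14 of 28 days, range 12 to 16) lies after re-randomisation, so a value on Period 2 treatment can be reported as Period 1 Week 24. This rests on the Table 2 limits and the 2-day visit window. For laboratory change from baseline it also depends on what last dose means.

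Neither gap reaches the primary results or the worst-grade laboratory tables. Both are worth closing because the affected outputs go into the abbreviated report and the correction is cheap.

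**What to change.** In SAP 8.1.2:

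- Use the scheduled-visit value when it exists. Use unscheduled or early-termination values only to fill a missing visit. Keep the highest grade in the window for the PCS tables.
- For re-randomised patients, end the Week 24 window at the first Period 2 dose.
- Count Period 2 windows from the Period 2 start date. The first safety window (Week 4) should run from Period 2 Day 2 to Day 43. The later ones follow the existing midpoint rule: Days 44–71, 72–99, 100–127, 128–155 and 156–183. The Part B rows should not be copied unchanged. Their Week 4 window opens on Day 23 because Part B has a Week 2 visit, and Period 2 has none, so Period 2 Days 2 to 22 would map to no visit.

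It would help to state in SAP 9.5 which last dose the on-treatment filter means. The SALT windows can keep their width.

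The cost is a revised Table 2 and minor reprogramming, with no change to data collection. The small downside is that unscheduled values would appear in by-visit tables only when the scheduled value is missing. They would remain in the listings and the PCS tables.

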Less than 11.5 g/dL	Interrupt dose until recovered to greater than 12 g/dL and resume dosing at previous dose
Platelet Count	Dose Adjustment
Less than 75 x 10 ⁹ /L	Interrupt dose until recovered to greater than 100 x 10 ⁹ /L and resume dosing at previous dose
Greater than 750 x 10 ⁹ /L	Interrupt dose until recovered to less than 600 x 10 ⁹ /L and resume dosing as prescribed by the Investigator

Upon dose interruption, the parameters that triggered the interruption should be monitored at least weekly until either: 1) recovery above the threshold for dosing resumption is achieved, or 2) a 21-day dose interruption period has elapsed, at which time a discussion between the PI and the Medical Monitor should occur to evaluate whether or not the subject should discontinue treatment permanently. In the case of severe neutropenia (neutrophil counts less than 0.5 x $10^9/L$) patient should interrupt dose **immediately** and repeat CBC with differential within 72 hours. The Medical Monitor should be contacted and a hematology consult should be made if appropriate. Permanent discontinuation of treatment should occur upon repeat confirmation of value. Patients who discontinue treatment due to lack of acceptable recovery of parameters should continue to be followed for all safety and efficacy assessments through the completion of the 24-week treatment period, and will have all endpoints (including efficacy) collected accordingly.

Subjects with both a positive SARS-CoV-2 test (antigen or antibody) AND signs or symptoms consistent with SARS-CoV-2 infection should immediately interrupt dosing with study drug. Dose interruption should continue until symptoms subside (it is not necessary to have a negative SARS-CoV-2 test result). If symptoms do not subside within a 21-day dose interruption period, a discussion between the PI and the Medical Monitor should occur to evaluate whether or not the subject should discontinue treatment permanently. Signs and symptoms include, but are not limited to: fever or chills, cough, shortness of breath or difficulty breathing, fatigue, muscle or body aches, headache, new loss of taste or smell, sore throat, congestion or runny nose, nausea or

vomiting, diarrhea, trouble breathing, persistent pain or pressure in the chest, new confusion, inability to wake or stay awake, bluish lips or face.

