Clinical laboratory variables will be presented in 3 ways. First, change from Baseline to each scheduled assessment will be summarized descriptively. Baseline will be defined as the laboratory value obtained before the first dose of study drug on Day 1(Part A, Period 1); if Day 1 values are unavailable, then values obtained at the Screening Visit will be used.

Second, treatment-emergent potentially clinically significant (PCS) laboratory values will be identified. Potentially clinically significant values are defined as those that meet Grade 3 or Grade 4 toxicity criteria from the CTCAE criteria. Treatment-emergent PCS laboratory values are those in which the baseline value is not PCS and the post-baseline value is PCS.

Third, treatment-emergent adverse events that result in dose interruption will also be identified.

The mean change from Baseline to each scheduled assessment will be summarized descriptively by dosing regimen for each clinical laboratory variable specified in this protocol.

The number and percentage of patients with Abnormal, clinically significant laboratory values (per Investigator judgment) and the number and percentage of patients with treatment-emergent PCS laboratory values will be summarized by dosing regimen for each clinical laboratory variable.

Vital Signs

The mean change from Baseline to each scheduled assessment will be summarized descriptively by dose group for each vital sign variable specified in this protocol.

Baseline will be defined as the last vital sign value obtained before the first dose of study drug on Day 1; if Day 1 values are unavailable, then values obtained at the Screening Visit will be used.

Electrocardiogram

The change from Baseline in electrocardiogram intervals (PR, QT, QTcF, QRS, and RR) to each scheduled assessment will be summarized descriptively by dose group.

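### The latest-in-window rule in SAP 8.1.2 lets repeat blood counts displace the scheduled out-of-limit value in the by-visit abnormal tables and the hematology box plots

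*SAP*

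**What the plan says.** SAP 8.1.2 treats the two kinds of visit differently. On planned visits: "For scheduled visits, there will be no reassignment of the analysis visit based on date". On the others: "Unscheduled visits and early termination visits will be reassigned based on the analysis windows in the below table and the schedule of events". One default then decides which record is summarized: "The latest assessment in a window will be selected as the visit used in summaries, unless otherwise specified".

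Protocol 10.2.1 is a systematic source of unscheduled hematology draws. Before a dose interruption, except in severe cases, "hematology parameters should be confirmed with repeat testing at an Unscheduled Visit within 72 hours". Once dosing is interrupted, "the parameters that triggered the interruption should be monitored at least weekly until either" the count recovers or 21 days pass.

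SAP 9.5 sets its own selection rule for one laboratory analysis only: treatment-emergent potentially clinically significant (PCS) values use the highest CTCAE grade in the window. The mean-change tables, the by-visit abnormal-value tables (14.3.4.7 to 14.3.4.9) and the figures have none. On the figures, SAP 9.5 says "box plots of hemoglobin, platelets, and neutrophils will also be provided with dose interruption limits included as reference lines". For mean change, Protocol 13.4.5 says "First, change from Baseline to each scheduled assessment will be summarized descriptively".

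**The concern.** A latest-record rule does little harm when the extra records arise for reasons unrelated to the result. Here many of them exist because the scheduled result was out of limits. Selection then depends on the outcome: an extreme value prompts a repeat, the repeat is later, and the later value is the one summarized. Both regression to the mean and recovery off drug make it less extreme on average.

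The by-visit displays of extremes suffer most. The box plots carry the interruption limits as reference lines so that a reader can see how often counts cross them, and the rule tends to remove those crossings. The Part A figures and the Part A hematology mean-change and abnormal-value tables are all marked in SAP Appendix 15.4 for the abbreviated report that supports the NDA.

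**Working it through.** **1. Windows (SAP Table 2, safety columns).** Width = upper − lower + 1; reach = upper − target.

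| Visit | Lower / target / upper | Width (days) | Reach past target (days) |
|---|---|---|---|
| Week 2 | 2 / 15 / 22 | 22 − 2 + 1 = 21 | 22 − 15 = 7 |
| Week 4 | 23 / 29 / 43 | 43 − 23 + 1 = 21 | 43 − 29 = 14 |
| Week 8 | 44 / 57 / 71 | 71 − 44 + 1 = 28 | 71 − 57 = 14 |

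The upper bounds are midpoints between adjacent targets: (15 + 29)/2 = 22, (29 + 57)/2 = 43, (57 + 85)/2 = 71. Later visits repeat the Week 8 pattern through Week 48 (324 / 337 / 351), and Part B repeats Weeks 2 to 24. The table is internally consistent.

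**2. Where the repeats fall.** Scheduled visits may be 2 days either side of target (Protocol Table 1, notes 2 and 5).
- +3 days (72-hour repeat): at latest target + 2 + 3 = target + 5. This is inside every window, including Week 2, and later than the scheduled draw.
- +7 days: at latest target + 9. Inside from Week 4 on; at Week 2, inside only if the visit was on or before target.
- +10 days (one week after the repeat): at latest target + 12. Inside from Week 4 on.
- +14 days: inside from Week 4 on if the visit was on or before target.
- +17 days: at earliest target + 15. Outside; it falls in the next window and is superseded if that scheduled visit takes place.

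**3. Example (assumed values, female hemoglobin, limit 10 g/dL).** Scheduled Day 57, 9.8; repeat Day 60, 9.9; weekly draw Day 67, 10.2. All three lie in Days 44 to 71. The latest rule shows 10.2, above the line. The scheduled value, also the worst in the window, is 9.8, below it.

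**4. Which summaries are exposed.** The on-treatment filter in SAP 9.5 applies to change from baseline and removes values after the last dose. A patient who resumes dosing has a later last dose, so draws during the interruption stay eligible. The filter is not stated for the box plots or abnormal-value tables. I assume the box plots are by visit; the SAP names no other basis.

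**5. Size, by simulation.** The documents give no hemoglobin distribution, so every input is assumed except the 10.5 g/dL screening threshold and the 10 g/dL limit:
- True baseline T ~ N(μ, 0.9²), μ = 12.0 or 12.5; patient kept if T + e > 10.5
- Scheduled S = T − 0.6 + e; repeat R = T − 0.6 + e
- Later in-window draw L = T − 0.6 + ρ + e, with recovery ρ from 0 to 0.6 g/dL
- Each e is an independent N(0, 0.5²)

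The value shown is S if S ≥ 10 and otherwise R. With a later draw, L replaces R when R is also below 10.

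| | μ = 12.0 | μ = 12.5 |
|---|---|---|
| Scheduled values below 10 | 5.1% | 2.1% |
| Of these, lost with the repeat alone | 65% | 71% |
| Values still shown below 10 | 5.1% × 0.35 = 1.8% | 2.1% × 0.29 = 0.6% |
| Lost with one later draw, ρ = 0 to 0.6 | 82% to 94% | 86% to 96% |
| Upward shift in visit mean, all cases (g/dL) | 0.03 to 0.05 | 0.01 to 0.02 |

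In this model the repeat is lower than the scheduled low value in about 15% to 17% of cases, so the direction holds on average and not for every patient.

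**6. A Period 2 arm of about 25.** One replaced patient is 1/25 = 4% of the arm. If that value rises by 0.3 to 1.5 g/dL, the visit mean rises by 0.3/25 = 0.012 to 1.5/25 = 0.06 g/dL.

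**The case against.** The strongest reply is that the safety information is not lost, and most of that stands. The PCS tables take the worst grade in the window. A neutrophil count between 0.5 and 1 × 10⁹/L, which Protocol Table 3 labels Grade 3, is therefore still counted if baseline was not PCS. Protocol 12.1 makes a laboratory abnormality that requires interruption an adverse event, and SAP 9.3 tabulates events leading to interruption. SAP 9.2 counts patients with at least one interruption, and the listings keep every value. The clearest gap is hemoglobin: PCS there means Grade 3 or higher, and the documents do not tie that grade to the interruption limit.

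A second reply is that the latest-value rule was meant only to choose among unscheduled draws. Table 2 is titled for unscheduled and early termination visits, and SAP 9.5 speaks of change to each scheduled visit. That reading is possible but is not what the sentence says, since it ranks all assessments in a window without distinction. If it was the intent, stating it costs nothing.

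A reader might also infer more than the documents support:
- **That almost every crossing disappears.** This needs full recovery to be seen inside the window. The confirmatory repeat normally precedes interruption, so with a repeat at +3 days, Day 14 of interruption is about visit + 17, outside the window.
- **That the bias always favours the drug, or concerns only low counts.** A repeat can be worse, high platelets also trigger interruption, and other unscheduled visits are at the investigator's discretion.
- **That the repeat is compulsory.** Protocol 10.2.1 says it should be done.
- **That each vanished point was an interruption.** In the simulation 65% to 71% of low values are not confirmed on repeat.

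**Conclusion.** The point holds for the by-visit abnormal-value tables and for the box plots drawn against the interruption limits. As SAP 8.1.2 is worded, a 72-hour repeat always lands in the same safety window as the scheduled draw and displaces it. The expected effect is toward less extreme values, for low counts and for high platelets.

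Under the assumed female hemoglobin inputs, roughly two thirds or more of scheduled crossings leave the plot. The mean-change tables are affected only trivially. The percentages rest on assumed means, variances, on-drug fall and recovery; the window arithmetic does not. The documents do not support a claim that cytopenia would go unreported, because the PCS, adverse event, exposure and listing outputs are untouched. In a descriptive study this should be corrected, but it does not threaten the trial's conclusions.

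**What to change.** Leave the SAP 8.1.2 sentence as it is, including its closing proviso. The PCS highest-grade rule depends on that proviso, and 8.1.2 also governs efficacy visits, which need not change. Add to SAP 9.5:

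> *For by-visit laboratory summaries (mean change, abnormal values and box plots), the scheduled-visit value is used where it exists. An unscheduled or early-termination value is used only if the scheduled value is missing, taking the one closest to the target day (the later if tied). The highest-grade rule for PCS values is unchanged.*

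Optionally, show each patient's worst on-treatment hemoglobin, neutrophil and platelet value per Part/Period in Figures 14.3.4.1 to 14.3.4.3 (for platelets, both lowest and highest).

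The cost is a short SAP addition and a change to the record-selection flag, with no new data. The downside is that the plots and abnormal counts will look slightly less favourable.
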